Study Objectives	1. Primary objective is to estimate the clinical response as quantified by irRECIST 1.1 to hypofractionated radiotherapy with nelfinavir and anti-PD1/PDL1 immunotherapy. 2. Secondary objectives are to evaluate late toxicity, immune-related clinical responses and immune pharmacodynamic changes hypofractionated radiotherapy with nelfinavir and anti PD1/PDL1 immunotherapy
Diagnosis and Main Inclusion Criteria	Patients with previously untreated or previously treated metastatic melanoma, NSCLC, or renal cell carcinoma with bone, lung, liver, or subcutaneous or nodal involvement but without evidence of brain involvement. Patients who have previously been treated with radiation will be included in the study, so long as a suitable plan for treatment can be developed. Patients who have received prior immunotherapy will be included in the study and enrolled into a separate stratum.
Study product, dose, route, regimen	Hypofractionated Image Guided Radiation Therapy. Three fractions of 800cGy each given over 3-14 days. Pembrolizumab, Nivolumab, or Atezolizumab per standard dosing and schedule. Nelfinavir: 1250 mg PO BID administered for 7 – 14 days prior to start of immunotherapy, for a total of 11-12 weeks.
Duration of administration	Radiation treatment to be delivered over 3-14 days with concurrent Nelfinavir and Immunotherapy. Subjects will take nelfinavir for a total of 11-12 weeks. Immunotherapy will continue per the FDA-approved dosing schedule.
Reference Therapy	FDA-approved PD-1 or PD-L1 inhibitors
Number of trial subjects	The expected accrual rate = 30 pts/yr. The protocol is designed for a maximum total of 120 patients (10 patients per year for melanoma and 10 patients per year for NSCLC and 10 patients per year for RCC).
Study Duration	The expected total study duration is 4 to 4 1/2 years needed to complete accrual.
Statistical Methodology	This is a stratified phase II study of hypofractionated radiotherapy combined with immunotherapy for previously untreated or previously treated metastatic melanoma, NSCLC, and renal cell carcinoma patients. Phase II is stratified by histology and whether or not the patient has received prior immunotherapy. We will also collect serum for correlative studies.

Table of Contents

1.0	INTRODUCTION TO THE PROTOCOL	6
1.1	Introduction.....	6
1.2	Preclinical Data.....	7
1.3	Clinical Data to Date.....	10
1.4	Reference Therapy: PD-1 and PD-L1 Inhibitors.....	12
1.5	Dose Rationale	15
1.6	Other Agents.....	15

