
[figure not shown]
The primary objective of this clinical trial is to determine whether hypofractionated radiotherapy and PI-3k inhibition using Nelfinavir can improve upon standard-of-care immunotherapy by targeting the PD-1 receptor in melanoma, renal cell carcinoma, and non-small cell lung cancer. Since the time of this protocol's original development, the Food and Drug Administration has rapidly given approval to additional drugs that belong to the same class as nivolumab (PD1/PD-L1 inhibitors) with *some overlapping* clinical indications for melanoma, non-small cell lung cancer, and renal cell carcinoma. These drugs currently include pembrolizumab [49-52] for melanoma and NSCLC, atezolizumab [53-60] for NSCLC, with FDA-approval pending for durvalumab [61-64]. These drugs all have similar clinical efficacy

and toxicity profiles to nivolumab [65-69] in the setting of melanoma (response rates 30-40%) [50, 52], non-small cell lung cancer (response rates 30-40%) [49, 53], and renal cell carcinoma (~25%) [70]. These drugs have varying treatment schedules allowing the physician and patient greater flexibility to tailor the immunotherapy regimen to their needs and circumstances.

Currently, there is no direct comparison data to indicate the superiority of one PD1/PDL1 antibody over another. The available agents are considered equivalent in their applicable settings. There is no rigid order of prioritization. In the absence of other factors, our institution plans to select pembrolizumab as the first-choice agent, due to its preferred 3-week scheduling over the 2-week scheduling of nivolumab, for melanoma and NSCLC patients enrolled on this clinical trial. Pembrolizumab and nivolumab are both preferred over atezolizumab because they have been more extensively studied and characterized. Certain factors arise that may lead to the selection of nivolumab (for melanoma or NSCLC) or atezolizumab (NSCLC), including a patient's individual insurance approval as well as the continuation of previously-started PD1 therapy among patients in the PD1 refractory cohort. See *Section 3.1 Immunotherapy Reference Therapy*

Nelfinavir: There are ample data available regarding the use of NFV in humans [37]. The following is an excerpt of the key features.

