4.0 SUBJECT ELIGIBILITY

4.1 Inclusion Criteria

4.1.1 Disease eligibility and Stage

- Histologically confirmed diagnosis of melanoma, NSCLC, or renal carcinoma.
- Previously treated or previously untreated stage IV melanoma, stage IV or recurrent lung cancer, and metastatic renal cancer by AJCC staging criteria
- Presence of a lesion that is suitable for hypofractionated radiotherapy

- 4.1.2 Disease measurement specifications
- 4.1.3 **Subjects must have measurable disease by RECIST criteria independent of the lesion to be irradiated.** Prior checkpoint inhibitor immunotherapy or chemotherapy is allowed as long as the last dose was received >14 days prior to enrollment.
- 4.1.4 Age ≥ 18
- 4.1.5 ECOG 0-2 (see Appendix 14.2)
- 4.1.6 Acceptable marrow function and hematologic indices for PD1/PDL1 immune checkpoint inhibitor and nelfinavir as per standard of care.
- 4.1.7 Ability to understand and the willingness to sign a written informed consent document.

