4.2 Exclusion Criteria

- 4.2.1 Subjects who have had immunotherapy, chemotherapy, or radiation therapy within 14 days (6 weeks for nitrosoureas or mitomycin C) prior to entering the study or those who have not recovered from adverse events due to agents administered more than 4 weeks earlier.
- 4.2.2 Subjects may not be receiving other investigational agents.
- 4.2.3 Patients with untreated/active brain metastases as documented by CT or MRI within 2 months of study enrollment. By active brain metastases- we mean- actively symptomatic brain metastases requiring steroids.
- 4.2.4 Allergy or intolerance to nelfinavir or selected PD1/PDL1 immune checkpoint inhibitor.
- 4.2.5 Patients requiring steroids or other immunosuppressive therapy. Low-dose or topical steroids are allowable if being used as replacement therapy.
- 4.2.6 Patients receiving anti-retroviral therapy or other agents that are contra-indicated with nelfinavir due to drug-drug interactions.*
- 4.2.7 Pregnant or lactating patients.
- 4.2.8 Prior radiation that precludes delivery of hypofractionated radiotherapy.

* For a study regarding the safety and efficacy of high dose nelfinavir on patients with Kaposi's Sarcoma (KS), exclusion criteria included participants who were receiving any "strong inhibitors or inducers of cytochrome P450, family 3, subfamily A (CYP3A) or cytochrome P450, family 2, subfamily C, polypeptide 19 (2C19)"

Strong Inhibitors of CYP3A4:

- Antibiotics: clarithromycin, erythromycin, telithromycin, troleandomycin
- HIV: non-nucleoside reverse transcriptase inhibitors (delavirdine, nevirapine), protease inhibitors (ritonavir, indinavir, lopinavir/ritonavir, saquinavir), cobicistat-boosted antiretrovirals (e.g., elvitegravir); NOTE: Clinical trials have demonstrated that there are no clinically significant drug-drug interactions between nelfinavir and the following antiretrovirals:

efavirenz (strong CYP3A4 inhibitor), etravirine (strong CYP3A4 inhibitor); therefore, these antiretrovirals will not be excluded.

- Antifungals: itraconazole, ketoconazole, voriconazole, fluconazole, posaconazole
- Antidepressants: nefazodone
- Antidiuretic: conivaptan
- GI: cimetidine, aprepitant
- Hepatitis C: boceprevir, telaprevir
- Miscellaneous: seville oranges, grapefruit, or grapefruit juice and/or pomelos, star fruit, exotic citrus fruits, or grapefruit hybrids.

Strong Inducers of CYP3A4:

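### Exclusion 4.2.4 covers intolerance to the selected PD-1/PD-L1 inhibitor only, so a melanoma or NSCLC patient with a resolved Grade 4 immune-related event on another agent of the class is not barred

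*Combined protocol and SAP*

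**What the plan says.** Patients already treated with a checkpoint inhibitor are part of the trial by design. The synopsis (Diagnosis and Main Inclusion Criteria) states: "Patients who have received prior immunotherapy will be included in the study and enrolled into a separate stratum". Section 4.1.3 sets the one condition on that earlier treatment: "Prior checkpoint inhibitor immunotherapy or chemotherapy is allowed as long as the last dose was received >14 days prior to enrollment".

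Three exclusions in 4.2 could bear on toxicity from an earlier inhibitor:

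- 4.2.1 excludes "those who have not recovered from adverse events due to agents administered more than 4 weeks earlier".
- 4.2.4 excludes "Allergy or intolerance to nelfinavir or selected PD1/PDL1 immune checkpoint inhibitor".
- 4.2.5 excludes "Patients requiring steroids or other immunosuppressive therapy", with an allowance for low-dose or topical steroids used as replacement.

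On the choice of agent, 1.4 says of melanoma and NSCLC: "In the absence of other factors, our institution plans to select pembrolizumab as the first-choice agent". It names two factors that may lead elsewhere, insurance approval and "the continuation of previously-started PD1 therapy among patients in the PD1 refractory cohort", and it says there is no rigid order of priority. It also describes the drugs as alike in efficacy "and toxicity profiles to nivolumab". The dosing tables in 3.1 list pembrolizumab and nivolumab for melanoma, all three agents for NSCLC, and nivolumab alone for RCC.

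For events on study, 6.4 calls for permanent discontinuation after a life-threatening immune-related event. The table in 6.3.8 does the same for Grade 4 events, with an exception for endocrinopathy controlled by hormone replacement.

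**The concern.** The word *selected* ties the intolerance exclusion to the agent the patient will receive in the trial. Where more than one agent is available, a severe reaction to one of them does not count against entry on another. The protocol treats the agents as similar in toxicity, so there is no stated reason to expect the second to be safer for that patient.

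What is at stake is patient safety. A patient with a known life-threatening immune reaction could be given another drug of the same class, now together with nelfinavir and radiation. Section 7.1 acknowledges that the combined effects of the inhibitor and nelfinavir have not been fully studied. Eligibility criteria exist so that a decision of this kind does not depend on how one investigator reads one word.

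**Working it through.** No arithmetic decides this point, and the plan gives no figure to reproduce. The check is to take one defined patient through the criteria and then compare the result with the on-study rules.

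**The patient.** Melanoma or NSCLC; earlier PD-1/PD-L1 agent A permanently stopped for a Grade 4 immune-related event; event resolved; off steroids; last dose more than 14 days before enrolment; agent B selected for the trial.

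**Step 1. Entry criteria that could catch the earlier event.**

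| Section | What it tests | Result for this patient |
|---|---|---|
| 4.1.3 | Time since last dose | Met; the reason for stopping is not asked |
| 4.2.1 | Adverse events not yet recovered, and the washout | Not excluded; recovered and past washout |
| 4.2.4 | Intolerance to nelfinavir or to the agent selected | Not excluded; the intolerance is to A, and B is selected |
| 4.2.5 | Present need for steroids or immunosuppression | Not excluded |

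The remaining exclusions concern other investigational agents, brain metastases, interacting drugs, pregnancy or lactation, and prior radiation. None addresses a past immune-related event.

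**Step 2. Can B differ from A?** Yes. Section 3.1 lists two agents for melanoma and three for NSCLC. Section 1.4 makes continuation of the earlier agent one factor that may guide the choice and does not require it. With pembrolizumab preferred, a patient who earlier received nivolumab or, in NSCLC, atezolizumab has a plausible route to a switch. The factors named in 1.4 are not presented as a complete list, and prior toxicity is not among them. RCC is left out of the point because only nivolumab is listed for it. A repeat of nivolumab would be caught by 4.2.4.

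**Step 3. The same event on study.** Section 6.4 would permanently stop the inhibitor. So would 6.3.8, which states its action for PD-1/PD-L1 inhibitor immunotherapy generally. Neither section is linked to eligibility.

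**Step 4. Size.** From 11.1, each of the six cohorts has 20 patients. The refractory melanoma and refractory NSCLC cohorts together give 2 × 20 = 40. That is a ceiling on who could be affected, not an estimate. The documents give no rate of earlier Grade 4 immune-related events, of recovery from them, or of switching agent, so no count follows.

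**The case against.** **The deciding text may be out of sight.** How a pretreated patient's agent is chosen belongs to the Selection Pathway in 3.1, and only its heading can be read. If the pathway returns such patients to their earlier agent, 4.2.4 already excludes them. This stands as a caveat. It does not remove the point, because the heading announces a site-preference order and 1.4 disclaims any rigid priority. What can be read describes a preference list, not an entry bar.

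**The cohorts are for *refractory* disease.** Sections 2.1.1, 2.2 and 11.1 use that word, and a patient stopped for toxicity without progression may fit no cohort. This narrows the group. It does not close the gap: the term is undefined, it is not a criterion in section 4, the synopsis admits patients with prior immunotherapy, and a patient who stopped for toxicity and later progressed would fit it.

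**The on-study rules may also be agent-specific.** Section 6.3.5 speaks of the patient's selected inhibitor, and 6.4 can be read as meaning the drug in use. Neither discusses a switch within the class. This is fair, and it is why a reader should not infer that the protocol contradicts itself. The on-study rules govern on-study events; entry after an earlier event is simply not addressed.

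**An investigator would decline such a patient, or read *intolerance* as class-wide.** Possibly, but neither is written down.

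**A Grade 4 line does not match 6.3.8.** That section also permanently stops treatment for most related Grade 3 non-skin events. This is true. The proposed clause is narrower on purpose, because re-exposure after a resolved Grade 3 event is more debatable and can be left to the sponsor.

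**Conclusion.** The gap is real on the readable text, and closing it is a cheap improvement. It is confined to previously treated melanoma and NSCLC patients who switch agent within the class after a resolved Grade 4 immune-related event. Several conditions must coincide, so it should be regarded as infrequent; the number cannot be derived. The conclusion assumes that 4.2.4 is applied as worded and that the unreadable pathway in 3.1 does not already settle the matter.

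Two stronger inferences are tempting and are not supported:

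- **That recurrences would distort the hepatotoxicity hold rule in 11.3.** Quantifying this needs a background Grade 4 rate and a recurrence rate. Section 11.3 gives historical rates for Grades 3 and 4 combined and no recurrence rate, and the earlier event need not have been hepatic. No effect on the rule is claimed.
- **That safety reviewers would fail to recognise a recurrence.** Section 11.3 names prior exposure to the class as something to consider after a related Grade 5 event, but that list is not exclusive. Section 7.4 requires a written narrative for serious adverse events, with supporting diagnostic information.

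**What to change.** Add to the end of 4.2.4: *or prior permanent discontinuation of any PD-1/PD-L1 inhibitor for a life-threatening (Grade 4) immune-related event, except endocrinopathy controlled by hormone replacement.* The exception follows the one already in 6.3.8. Add a registration field recording why any earlier PD-1/PD-L1 inhibitor was stopped. Whether to extend the bar to resolved Grade 3 events is for the sponsor to decide. If the Selection Pathway in 3.1 already prevents such a switch, a cross-reference to it in 4.2.4 would serve instead.

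The cost is one clause, one data field and a few patients not enrolled. Sample size, endpoint and analysis do not change. If a share x of candidates for the two cohorts were excluded and referral stayed constant, the time to fill them would be multiplied by 1/(1 − x). With x assumed between 1% and 5%, that is 1/0.99 = 1.01 to 1/0.95 = 1.05. These values of x are illustrative and do not come from the documents.

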4.3 Criteria for Removal/Withdrawal from Treatment

- 4.3.1 Subjects may be removed from this study at any time at their discretion. Subjects may also be removed from this protocol if they develop any untoward side effects from the study medication. In addition there are stopping rules in place for lack of efficacy and excessive toxicity as detailed in the statistical section.
- 4.3.2 Disease progression will be clinically determined by the principal investigator. Patients who show disease progression will be taken off of the study.
- 4.3.3. Extraordinary Medical Circumstances. If at any time the constraints of this protocol are detrimental to the subject's health, the subject will be removed from protocol therapy. In this event, the reasons for withdrawal will be documented.

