6.6 Duration of Therapy

Reference PD1/PDL1 inhibitor therapy ends at the time of progression (as defined by Response Evaluation Criteria in Solid Tumors (RECIST) version 1.1 (irRECIST v1.1) by physical examination and radiographic assessment, primarily CT scan, immune response criteria and/or loss of clinical benefit as assessed by the investigator). The study period is defined from the time of consent through the follow-up period or end of service. The last follow-up appointment occurs 6-months after the last dose of nelfinavir. Patients will be seen prior to end of service as per standard of care. Additional endpoints will include overall survival and safety.

6.7 Rationale for Allowing Patients to Continue PD1/PDL1 immune checkpoint inhibitor Treatment until Loss of Clinical Benefit

Conventional response criteria may not adequately assess the activity of immunotherapeutic agents because progressive disease (by initial radiographic evaluation) does not necessarily reflect therapeutic failure. Because of the potential for pseudo progression/tumor immune infiltration, this study will allow patients to remain on PD1/PDL1 immune checkpoint inhibitor after apparent radiographic progression, provided the benefit-risk ratio is judged to be favorable. Patients should be discontinued for unacceptable

toxicity or symptomatic deterioration attributed to disease progression as determined by the investigator after an integrated assessment of radiographic data, biopsy results (if available), and clinical status. Patients who show evidence of clinical benefit will be permitted to continue PD1/PDL1 immune checkpoint inhibitor after RECIST v1.1 criteria for progressive disease are met if they meet all of the following criteria:

- Evidence of clinical benefit as assessed by the investigator
- Absence of symptoms and signs (including worsening of laboratory values, e.g., new or worsening hypercalcemia) indicating unequivocal progression of disease
- No decline in ECOG performance status that can be attributed to disease progression
- Absence of tumor progression at critical anatomical sites (e.g., leptomeningeal disease) that cannot be managed by protocol-allowed medical interventions
- Patients for whom approved therapies exist must provide written consent to acknowledge deferring these treatment options in favor of continuing study treatment at the time of initial progression

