6.8 Off Treatment Criteria

Patients will be removed from protocol therapy when any of the criteria listed in Section 6.3.8 applies. The source document will give the reason for ending protocol therapy and the date the patient was removed from treatment. All patients who discontinue treatment should comply with protocol specific follow-up procedures as outlined in Appendix 14.4. There are two exceptions to this requirement:

- Patient starts a new anti-cancer therapy and/or receives additional radiation treatment prior to follow-up procedures
- Patient withdraws consent for all study procedures or loses the ability to consent freely.

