6.9 Duration of Follow-Up

Patients will be followed after completion or removal from protocol treatment at two protocol-mandated time points. The first follow-up will occur 1 month after last dose of Nelfinavir (+/- 2 weeks), while the second follow-up will occur 6 months from date of enrollment (+/- 2 weeks). All patients who discontinue treatment should comply with the procedures below unless they meet the exceptions in Section 6.8:

- Physical Exam; ECOG
- Adverse Events Monitoring
- Concomitant Medication Monitoring
- Response Assessment by irRECIST 1.1
- Research Blood Collection
- Optional tumor biopsy

Survival follow-up will continue for 2 years from enrollment through office visits (scheduled at clinically indicated intervals, will vary by patient) and by review of medical record. Subjects may be contacted by phone call every 6 months to determine vital status.

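### Section 4.3.2 takes patients with progression off the study, which read literally contradicts the follow-up in Sections 6.8 and 6.9 and would bias overall survival upward; a one-sentence clarification cures it

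*Combined protocol and SAP*

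**What the plan says.** Section 4.3.2 first makes progression a clinical judgement of the principal investigator and then states: "Patients who show disease progression will be taken off of the study". It carries no exception and no cross-reference. The next item, 4.3.3, uses a different term for its own situation: "the subject will be removed from protocol therapy".

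Section 6.8 says: "All patients who discontinue treatment should comply with protocol specific follow-up procedures as outlined in Appendix 14.4". It allows two exceptions. One is "Patient starts a new anti-cancer therapy and/or receives additional radiation treatment prior to follow-up procedures"; the other is withdrawn consent or lost capacity to consent freely.

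Section 6.9 says: "Patients will be followed after completion or removal from protocol treatment at two protocol-mandated time points". These visits fall 1 month after the last nelfinavir dose and 6 months after enrollment. They include adverse events, response by irRECIST and research blood. The section then adds: "Survival follow-up will continue for 2 years from enrollment through office visits". Medical record review is also planned, and "Subjects may be contacted by phone call every 6 months to determine vital status".

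Section 2.3.2 censors overall survival (OS) at last contact for patients not known to have died. Section 6.10 lists reasons for leaving the study; progression is not among them, but the list is open-ended.

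**The concern.** A patient taken off the study at progression cannot also attend the later visits in 6.9 or be followed for survival to 2 years. The two instructions apply to the same patients and give opposite results, and the protocol does not rank them.

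What is at stake is mainly OS, which Section 2.1.2 lists as a secondary objective in every disease and prior-treatment cohort. Under the literal rule, the last contact for a patient who progresses is the progression date. Deaths after that date are not collected, and censoring is triggered by the very event that worsens prognosis. The Kaplan-Meier medians, landmark estimates and Cox models in Section 11.2 all assume that this does not happen. The safety, response and correlative data from visits after progression would go too.

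**Working it through.** No stated figure is in dispute. The check compares the texts, orders the scheduled dates, and works out the direction of the bias.

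**1. The rules side by side, for a patient with progression**

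| Section | Instruction | Exception for progression? |
|---|---|---|
| 4.3.2 | Leaves the study | This is the progression rule itself |
| 6.8 | Follow-up procedures after stopping treatment | No; two exceptions, on new therapy and on consent |
| 6.9, visits | Two visits, subject to the 6.8 exceptions | No |
| 6.9, survival | Followed to 2 years from enrollment | No |
| 6.10 | Open list of off-study reasons | Progression not named |

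A patient who progresses and starts a new anti-cancer therapy before the visits is exempt from them under 6.8, so for that patient the visits do not conflict with 4.3.2. The exemption in 6.9 is attached to the listed visit procedures and not to the survival sentence that follows them. The conflict over survival follow-up therefore remains for patients who switch therapy.

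**2. Whether the visits fall after progression**

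Inputs: nelfinavir starts 1-2 weeks before immunotherapy and runs 11-12 weeks (Section 6.1); the first scan is 12-14 weeks after immunotherapy starts (Section 9.2); visit windows are plus or minus 2 weeks (Section 6.9). Assumption: nelfinavir starts at enrollment.

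- First scheduled scan: (1 to 2) + (12 to 14) = week 13 to 16.
- First visit: (11 to 12) + about 4 = week 15 to 16, or week 13 to 18 with the window.
- Second visit: 6 months is about week 26, or week 24 to 28 with the window.

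Progression found at the first scheduled scan (week 16 at the latest) precedes the second visit (week 24 at the earliest). It may also precede the first visit. Note a of the treatment calendar gives a shorter scan interval of 10-12 weeks, which would bring progression forward and leave this order unchanged.

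**3. Direction of the OS bias**

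Let h0(t) be the death rate among patients alive without progression, h1(t) the rate among patients alive after progression, and w(t) the share of survivors at time t who have not progressed. The OS hazard is

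h(t) = w(t) × h0(t) + [1 − w(t)] × h1(t).

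If contact ends at progression, only patients without progression remain at risk, so Kaplan-Meier estimates the curve for h0(t) alone. With h1(t) > h0(t), which is the expected order in metastatic disease, h0(t) < h(t) and the OS curve is too high.

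**4. Size**

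The calculation needs h0, h1 and w for these six cohorts, and the documents give none of them. The survival medians in Section 1.3 come from locally advanced lung cancer treated with chemoradiotherapy and are not split at progression. No size can be derived.

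**The case against.** The strongest reply is that 4.3.2 is loose drafting and that 6.9 is plainly the operating rule. Section 4.3 is headed as covering removal from treatment. Item 4.3.1 speaks of leaving the study and leaving the protocol without care, including for side effects, where 6.8 clearly expects follow-up. Section 6.10 omits progression and ties loss to follow-up to failing to document survival after 2 years. OS is a stated objective. Study treatment is given at two named facilities (Section 6.0), and the principal investigator personally oversees all subjects (Section 12.0), so divergent practice is unlikely.

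Most of this stands as evidence of intent, and it is why the point is minor. It does not settle the text. Item 4.3.3 has a separate term for stopping treatment, 4.3.1 also covers genuine withdrawal from the study at the subject's wish, and 6.10 is open-ended and allows withdrawal at the investigator's discretion.

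Three stronger readings are tempting and are not supported:

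- *That 4.3.2 flatly contradicts treatment beyond progression.* Section 6.7 says "this study will allow patients to remain on PD1/PDL1 immune checkpoint inhibitor after apparent radiographic progression", but it requires continuing clinical benefit and no unequivocal signs of progression. Since 4.3.2 rests on clinical judgement, a patient who qualifies under 6.7 need not have progressed in the sense of 4.3.2. The two can be reconciled.
- *That survival data will in fact be lost.* Nothing in the documents shows that staff would apply 4.3.2 over 6.9.
- *That Section 9.2, by scheduling scans until progression, leaves an imaging gap.* Section 9.2 also allows scans as clinically indicated, 6.9 requires irRECIST at both visits, and note a of the calendar sets no stop at progression.

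**Conclusion.** The contradiction between 4.3.2 and Sections 6.8 and 6.9 is real on the wording, and no text resolves it. Applied literally, 4.3.2 would make OS censoring informative and bias the OS estimates upward in each cohort, and would drop visits after progression. The direction rests on mortality being higher after progression than before it. The size cannot be computed from the documents.

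A reader might infer that the primary result is compromised. It is not: the response thresholds and the 20 patients per cohort in Section 11.1 do not depend on contact after progression. OS carries no decision rule, and the harm does not arise if 6.9 is followed. Severity: minor.

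**What to change.** In 4.3.2, replace the instruction to leave the study with wording such as: *taken off protocol treatment (except as allowed in 6.7), with follow-up visits continuing per 6.8-6.9 and survival follow-up for 2 years per 6.9*. The two exceptions in 6.8 continue to apply to the visits. The mention of 6.7 is for consistency only.

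The cost is one amended sentence. It adds no procedures, because the visits, record review and 6-monthly calls are already in 6.9. No change to Section 9.2, the sample size or the decision rules is needed.
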